### **6.3.8.7 Glomerular Filtration Rate**

A limited number of sites only will simultaneously determine GFR with iohexol administration and blood sampling (considered the golden standard) to globally compare and assess correlation of GFR and calculated endogenous creatinine clearance. In addition, at these sites samples from the effluent from patients on RRT will be taken to assess exogenous (machine) creatinine clearance. Detailed instructions to these sites for iohexol and exogenous creatinine clearance are provided in Section 13.5.

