## **13.5 Appendix 5: Iohexol and Exogenous Creatinine Clearance Protocol (Including Pharmacodynamics) for Selected Sites Only**

### **13.5.1 Introduction**

Accurate measurement of glomerular filtration rate (GFR) is valuable for evaluating kidney function and nephrotoxicity in a variety of clinical research and patient care settings. Accurate GFR determinations are recommended to appropriately assess the value of pharmacotherapeutic interventions aimed at improving tubular microvascular hemodynamics, inflammation and slowing the progression of renal disease.

The measure mostly used for the determination of the kidney function is the creatinine clearance as proxy for GFR. However, creatinine clearance is not fully representative in unstable situations, such as acute kidney injury, because it is influenced by various factors (e.g., diet, muscle mass, physical activity, and excretion and resorption in the kidney) and therefore results of creatinine clearance can be an over- or under-estimation. Creatinine clearance is routinely used to determine the function of the kidneys irrespective of the drawbacks, since it is inexpensive, non-invasive, and easy to perform.

Marker compounds such as iothalamate, iohexol, or inulin have been used extensively to measure GFR. Although renal clearance of these markers during continuous infusion is considered the gold standard, simplified methods using limited sampling after intravenous bolus administration with and without urine collection have been proposed.

The GFR estimation methods using creatinine concentration have been described as unreliable in some subgroups of the general population, especially in patients with non-steady state renal function. As iohexol has the main characteristics of a convenient marker of GFR, its plasma clearance seems to be the best choice to determine GFR in controlled laboratory settings. Contrary to determination of renal clearance of inulin, iohexol plasma clearance does not require continuous intravenous infusion.

It is generally assumed that endogenous creatinine clearance is not influenced by continuous renal replacement therapy. In order to reliably determine potential changes in endogenous creatinine clearance, any change in creatinine clearance needs to be excluded. To evaluate if renal replacement therapy (RRT) has an effect on endogenous creatinine clearance, the exogenous creatinine clearance by RRT equipment will be assessed by measuring the

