### **13.5.5 Statistical Data Analyses**

#### **13.5.5.1 Iohexol and Creatinine Clearance**

Results from the measurement of iohexol and endogenous and exogenous creatinine clearance will be investigated in an exploratory manner with more details provided in the statistical analysis plan (SAP) (e.g., measured GFR, endogenous creatinine clearance in relation to exogenous creatinine clearance).

Iohexol clearance ( $Cl_{\text{Iohexol}}$ ), as a gold standard measure of GFR, will be correlated to creatinine clearance at the different time points in a subset of patients.

The  $Cl_{\text{Iohexol}}$  will be calculated by a 2-compartment model where  $Cl_{\text{Iohexol}} = \text{dose}/\text{area}$  under the curve from 0 to infinity, with extrapolation from 6 hours to infinity, and potentially a more refined model.

Only descriptive methods will be applied for assessing exogenous creatinine clearance.

Effective renal plasma flow will be correlated with the iohexol clearances and creatinine clearances.

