Results from the primary analysis for interim analysis at Part 1 and for Part 2 will include least square means for each treatment and the difference in least squares means between the treatment groups will also be presented along with the associated 95% CI. P-values will be presented for least square mean treatment differences. The one-sided p-value for the combined analysis will be presented with the sample sizes and one-sided p-values from the interim analysis at Part 1 and at Part 2.

Descriptive statistics for the primary endpoint and mean standardized endogenous creatinine clearance at Day 1 to Day 7 will also be presented in a summary table by

treatment. This will be presented for all four treatment groups for the ITT Combined, ITT part 1 Interim, PP Day 1-7 Part 1, and also for the optimal recAP dose and placebo treatment groups for the ITT Part 2 and PP Day 1-7 Part 2 Sets. Analysis on the PP Set will be used as a supplement to the ITT analysis. The ITT Part 1 Interim Set (for all four treatment groups) will also be produced to help check the assumption of the combined analysis that patients recruited in each part of the study belong to the same overall patient population.

The primary endpoint, AUC_{1-7} , and standardized endogenous creatinine clearance at Day 1 to Day 7 will be listed.

A time-course plot of standardized endogenous creatinine clearance with associated error bars on each day will be presented for the optimal recAP dose and placebo groups. This plot will be repeated three times using different selection criteria for the data based on data imputation and adjudication of creatinine clearance data:

- 1) Including only calculated values (i.e. no imputed values)
- 2) Including all (non-adjudicated) calculated and imputed values
- 3) Including only adjudicated calculated and imputed values

The combined ITT analysis primary endpoint summary and analysis will be repeated as a supportive sensitivity analysis, excluding patients who died before day 8, with SAS[®] output from Part 1 and Part 2 models included on the primary combined analysis output. Additionally, descriptive statistics for the primary endpoint and mean time-corrected endogenous creatinine clearance at Day 1 to Day 7 will be presented in a summary table for the ITT Combined Set by treatment group and subgroup category, defined in [Section 8.1.5](#).

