Iohexol plasma concentrations will be listed and summarized using descriptive statistics by timepoints. Iohexol PK parameters will be listed and summarized using descriptive statistics. These summaries will include the number of patients (n), mean, standard deviation (SD), coefficient of variation (CV), minimum, median, maximum, geometric mean, and geometric %CV, when applicable.

Iohexol clearance ($CL_{Iohexol}$), as a gold standard measure of GFR, will be correlated to creatinine clearance in a subset of patients using scatter plots.

Exogenous Creatinine Clearance

To evaluate if renal replacement therapy (RRT) has an effect on endogenous creatinine clearance, the exogenous creatinine clearance by RRT equipment will be assessed by measuring the creatinine concentration in the effluent and effluent volume during the 6 ± 1 hour urine collection interval. This will be only done by the sites participating in the Iohexol substudy.

Standardized exogenous creatinine clearance (mL/min) by the RRT equipment will be calculated by PPD Biostatistics using the following formula.

$$\frac{\text{Effluent Creatinine (mg/dL)}}{\text{Serum Creatinine (mg/dL)}} \times \frac{\text{Total effluent volume collected (mL)}}{\text{Stop date/time – Start date/time of effluent collection (min)}}$$

- The effluent creatinine (mg/dL) will be assessed by the laboratory conducting the Iohexol data.
- The serum creatinine (mg/dL) assessed by the central laboratory and used in the primary endpoint of endogenous creatinine clearance will be used to determine the standardized exogenous creatinine clearance.
- Per protocol, two blood samples are collected to evaluate the serum creatinine, one at the beginning of the urine sample collection and the other at the end of the urine sample collection. The average of these two serum creatinine measurements will be used in the formula above to assess the standardized exogenous creatinine clearance. In case there is only one serum creatinine sample available, then the serum creatinine concentration from that one sample will be used in the formula.
- The number of minutes from the start date/time to the stop date/time of effluent sample collection and the total effluent volume (mL) from the RRT equipment will be derived from data collected at site.

The time-corrected exogenous creatinine clearance will be listed for subjects who are on RRT in the Iohexol population.

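### The iohexol substudy plans only correlation shown as scatter plots, so it will not quantify how far creatinine clearance departs from GFR

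*SAP*

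**What the plan says.** Protocol section 6.3.8.7 has a limited number of sites measure GFR with iohexol "to globally compare and assess correlation of GFR and calculated endogenous creatinine clearance". The introduction to that appendix (13.5.1) explains why: in unstable kidney function "results of creatinine clearance can be an over- or under-estimation". Section 13.5.5.1 then says that iohexol clearance "will be correlated to creatinine clearance at the different time points in a subset of patients", describes the work as exploratory, and leaves the detail to the SAP.

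The SAP supplies that detail in section 8.3: iohexol clearance, "as a gold standard measure of GFR, will be correlated to creatinine clearance in a subset of patients using scatter plots". The sentence names no coefficient, test, paired difference, ratio, limits of agreement or identity line, and it drops the protocol's reference to separate time points.

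The other outputs are not paired. For iohexol, "Iohexol PK parameters will be listed and summarized using descriptive statistics". For creatinine, SAP 8.1.1 says that "standardized endogenous creatinine clearance at Day 1 to Day 7 will be listed".

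Iohexol is given on Day 1 and again on Day 7 or at ICU discharge, at the start of the 6-hour urine collection, so the two clearances cover the same interval. The Iohexol Set (SAP 4.3.6) has no planned size, and neither document sets an acceptance limit for the comparison.

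**The concern.** The question in protocol 13.5.1 is one of agreement: by how many mL/min, and in which direction, does creatinine clearance depart from GFR? The planned analysis answers a different question, namely whether patients with higher GFR also have higher creatinine clearance. A strong association is compatible with a large systematic error.

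What is at stake is interpretation. The primary endpoint is an average of creatinine clearance in mL/min, and the planning values (60, 69.5 and 79 mL/min) are on that scale. One primary objective is to support the Phase 3 program, so the size of an effect in terms of kidney function matters as well as its p-value. The substudy asks patients for up to two iohexol injections and repeated sampling, and the data could answer the question directly.

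**Working it through.** **1. No figure to reproduce for the substudy.** The documents give no sample size, target correlation or acceptable bias. All bias and error values below are assumptions.

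**2. Correlation ignores constant bias.** For any constants a and k > 0, corr(G, a + kY) = corr(G, Y). Take true GFR G with mean 60 and SD 49 mL/min, and unbiased creatinine clearance Y = G + error, with error SD 15. The mean and SD are borrowed from the planning values for the primary endpoint; the error SD is assumed.

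- r = 49 / √(49² + 15²) = 49 / 51.24 = 0.956.
- Mean bias d = mean of (creatinine clearance − GFR).
- Limits of agreement = d ± 1.96 × SD of the differences.
- Lin's concordance = 2·cov / (var₁ + var₂ + d²).

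| Assumed bias | r | Mean bias | Limits of agreement | Concordance |
|---|---|---|---|---|
| none | 0.956 | 0 | −29.4 to 29.4 | 4802/5027 = 0.955 |
| +30 mL/min | 0.956 | +30 | 0.6 to 59.4 | 4802/5927 = 0.810 |
| ×1.5 | 0.956 | +30 | −35.2 to 95.2 | 7203/9209.5 = 0.782 |
| ×0.6 | 0.956 | −24 | −66.3 to 18.3 | 2881.2/3922.4 = 0.735 |

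The SDs of the differences are 15, 15, √(0.25·2401 + 2.25·225) = 33.3 and √(0.16·2401 + 0.36·225) = 21.6. Simulation with 100,000 records gives r = 0.957 in all four rows and the same pattern elsewhere.

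**3. The correlation need not be high.** With lognormal GFR (log SD 0.6) and multiplicative error of log SD e, r = √[(exp(0.36) − 1) / (exp(0.36 + e²) − 1)]. For e = 0.2, 0.4, 0.6 and 0.8 this is 0.94, 0.80, 0.64 and 0.50. The bias factor cancels. The correlation therefore reflects patient spread and random error, and carries no information on constant bias in either direction.

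**4. Effect on the primary analysis.** A simulation of the main design used 30 per arm, selection of the best dose, Dunnett-adjusted closed testing, the inverse normal combination with 85 per arm and the futility rule, without site. It gives power of 79%, 81% and 86% for low-dose responses of 69.5, 60 and 79 mL/min (plan: 79% to 86%), and one-sided type I error of 2.5% (plan: 2.4%). Adding +20 mL/min to every arm, or multiplying every arm by 1.4, leaves power at 81%; with both applied, type I error stays at 2.5%.

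**5. Effect on interpretation.** A constant offset common to all arms cancels from the difference between arms and changes only absolute levels. A constant factor k does not cancel: GFR effect = creatinine clearance effect / k. For an observed 19 mL/min:

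- k = 0.6: 31.7 mL/min
- k = 1.0: 19 mL/min
- k = 1.4: 13.6 mL/min
- k = 1.5: 12.7 mL/min

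**6. Bias that differs between arms.** For a simple comparison of 115 per arm, SE = 49·√(2/115) = 6.46. A spurious 5 mL/min raises one-sided error from 2.5% to 1 − Φ(1.96 − 5/6.46) = 12%. Nothing in the documents says that such a bias exists; this is a reason to show agreement by arm where numbers permit.

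**7. Precision of an agreement analysis.** With difference SD 15, the 95% half-width for mean bias is 1.96·15/√n, or 6.6 mL/min at n = 20 and 4.6 at n = 40. For each limit of agreement it is about 1.71 times larger: 11 and 8 mL/min.

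**The case against.** The analysis is exploratory, at selected sites, and feeds no test or decision. The protocol's own aim includes assessing correlation, so the SAP delivers part of what was promised. All of this stands, and it keeps the point modest.

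The SAP names a plot, not a coefficient or a significance test. Both clearances can be shown in mL/min, so a large bias could be seen by eye. With a factor of 1.4 and log error SD 0.2, Φ(ln 1.4 / 0.2) = Φ(1.68), or about 95% of points, would lie above the identity line. A reader might infer that the plan cannot detect bias at all; that goes too far. What is missing is a measure of its size, and neither equal axes nor an identity line is specified to make it visible. Paired differences could also be derived later from the listed data, but they would then not be pre-specified.

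A reader might also infer that a high correlation is assured and would be taken as validation of the primary endpoint. The documents support neither step. Step 3 shows that r depends on an error size they do not give, and SAP 8.1.5 itself calls creatinine clearance highly variable. Neither document calls the substudy a validation or sets a pass criterion.

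Finally, an agreement analysis on the log scale alone would fail. SAP 8.1 sets clearance to 0 mL/min when urine volume is 0 mL, and to 1 mL/min when volume is below 30 mL per 24 hours. RRT also matters: SAP 8.3 derives iohexol clearance from plasma as dose over AUC, while the creatinine measure is urinary. Any removal of iohexol by the machine would then look like bias. Both objections stand and shape the fix.

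**Conclusion.** The point holds in a limited form. The only planned paired comparison describes association, and it does not quantify the over- or under-estimation that the protocol names as its concern. That conclusion follows from the texts and from the algebra in step 2, and does not depend on the assumed values.

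It is tempting to read this as a threat to the primary test. The documents and the check do not support that: a constant offset or factor common to all arms leaves power and type I error unchanged, and the planning effects are defined in creatinine clearance units. The consequence is for translating an effect into GFR, and its size depends on an unknown factor. Over assumed factors of 0.6 to 1.5, 19 mL/min of creatinine clearance corresponds to between 31.7 and 12.7 mL/min of GFR. A bias that varies with kidney function, RRT status or arm is not covered by this reassurance, and correlation alone would not characterise it.

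**What to change.** In SAP 8.3, Iohexol substudy:

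- Add the paired difference, creatinine clearance minus iohexol clearance in mL/min, with mean bias, 95% CI and limits of agreement, shown as a Bland-Altman plot.
- Report it separately for Day 1 and for Day 7 or ICU discharge, and by RRT status at the time of measurement; add a split by arm if numbers allow.
- Give the geometric mean ratio only as a supplement, for records with measured non-zero clearance, excluding values set to 0 or 1 mL/min by rule.
- Keep the scatter plots, on equal axes with the line of identity drawn.

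Protocol 13.5.5.1 already defers the detail to the SAP. The cost is one figure and one small table from data already collected, with no further samples. Limits of agreement will be wide in a small subset, especially after splitting by RRT status, and should be presented as descriptive.

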9.1. Adverse Events

An AE is defined as any untoward medical occurrence in a patient enrolled into a clinical study regardless of its causal relationship to study drug.

A Treatment emergent Adverse Event (TEAE) is defined as any event not present before exposure to study drug or any event already present that worsens in either intensity or frequency after exposure to study drug.

All AEs will be coded using MedDRA Version 16.1 or later.

9.1.1. Incidence of Adverse Events

Summaries of the total number of TEAEs and the number and percentage of patients with at least one TEAE will be provided by treatment group. Treatment emergent AEs will be presented by SOC and PT. At each level of patient summarization, a patient is counted once if the patient reported one or more events.

All AEs will be presented in a listing.

9.1.2. Relationship of Adverse Events to Study Drug

The investigator will provide an assessment of the relationship of the event to the study drug. The relationship of the event to the study drug will be characterized using the following classification and criteria:

- Unrelated: This relationship suggests that there is no association between the study drug and the reported event.
- Possible: This relationship suggests that treatment with the study drug caused or contributed to the AE; i.e., the event follows a reasonable temporal sequence from the time of drug administration or follows a known response pattern to the study drug, but could also have been produced by other factors.
- Probable: This relationship suggests that a reasonable temporal sequence of the event with drug administration exists and, based upon the known pharmacological action of the drug, known or previously reported adverse reactions to the drug or class of drugs, or judgment based on the investigator's clinical experience, the association of the event with the study drug seems likely. The event disappears or decreases on cessation or reduction of the dose of study drug.
- Definite: This relationship suggests that a definite causal relationship exists between drug administration and the AE, and other conditions (concurrent illness, progression/expression of disease state, or concurrent medication reaction) do not appear to explain the event. The event reappears or worsens if the study drug is re-administered.

TEAEs that are missing a relationship will be presented in the tables as "Definite".

The TEAE data will be categorized and presented by SOC, PT, and relationship in a manner similar to that described in [Section 9.1.1](#). In the TEAE relationship table, at each level of patient summarization, a patient is counted once for the most related event if the patient reported one or more events.

9.1.3. Severity of Adverse Event

The intensity of an AE refers to the extent to which an AE affects the patient's daily activities and will be rated as mild, moderate, or severe using the following criteria:

- Mild: These events require minimal or no treatment and do not interfere with the patient's daily activities.
- Moderate: These events are sufficiently discomforting to interfere with normal activities.
- Severe: These events interrupt a patient's usual daily activity and may require systemic drug therapy or other treatment. Severe events are usually incapacitating.

TEAEs that are missing severity will be presented in tables as "Severe" but will be presented in the data listing with a missing severity.

The TEAE data will be categorized and presented by SOC, PT, and severity in a manner similar to that described in [Section 9.1.1](#). In the table, at each level of patient summarization, a patient is counted once for the most severe event if the patient reported one or more events.

9.1.4. Serious Adverse Events

The seriousness of an AE should be assessed by the Investigator independently from the severity of the AE. A SAE is defined as any untoward medical occurrence that at any dose results in death, is life-threatening, is a congenital anomaly/birth defect, requires in-patient hospitalization or prolongation, or results in significant disability/incapacity.

Important medical events that may not result in death, be life-threatening, or require hospitalization may be considered SAEs when, based upon medical judgment, they may jeopardize the patient and may require medical or surgical intervention to prevent one of the outcomes listed above.

Serious treatment emergent adverse events (TEAE) will be presented in a table. They will be presented by SOC and PT in a manner similar to that described in [Section 9.1.1](#).

9.1.5. Adverse Events Leading to Treatment Discontinuation

A summary of TEAEs with a study drug action taken of “Treatment Withdrawn” will be presented in a table. They will be presented by SOC and PT in a manner similar to that described in [Section 9.1.1](#).

9.1.6. Death

For patients who died any time during the study or during follow-up, their cause of death will be categorized and presented by SOC, PT. A listing of all deaths and associated cause of death will be provided as well. All death will be coded using MedDRA Version 16.1 or later.

9.2. Laboratory Evaluations

Laboratory assessments not used for the efficacy analysis will be used for the safety analysis and be performed by the local laboratory. All summaries will be based on the units provided defined in the eCRF, no conversion will be done. Also, the out of normal range data will be presented.

Hematology and clinical chemistry assessments will be summarized according to the visits and will be assessed at Baseline, Day 1, 3, 5, 7, 14, 21 and 28. Shift tables presenting baseline and post-baseline values below, within, above or below the normal range (normal ranges as provided by the local laboratories), and count tables at each visit will be presented for hematology and clinical chemistry tests with numeric values below, within or above the normal range (normal ranges as provided by the local laboratories) by treatment group for patients in the Safety Set. The percentage will be based on the number of patients who have attended the visit.

Only scheduled assessments will be included in the laboratory summaries. In case of repeat values the last assessment will be used for pre-dose visits and the first value for post-dose visits.

